Any incidental findings on the ⁶⁴Cu-SAR-bisPSMA PET/CT scan(s) that are of potential clinical relevance and are not directly associated with the objectives of the protocol should be evaluated and handled by the investigator as per standard medical/clinical judgment.

The processes for image acquisition, transmittal, and interpretation, including the list of regions and subregions to be assessed on the ⁶⁴Cu-SAR-bisPSMA PET/CT are detailed in the Image Acquisition Manual.

7.3.2.2 ⁶⁴Cu-SAR-bisPSMA PET/CT Central Interpretation

The central reading center will receive and evaluate the ⁶⁴Cu-SAR-bisPSMA PET/CT scans. The scans will be interpreted by three different independent blinded readers in a random order at separate reading sessions. Central readers will be blinded as described in Section 4.3. Computed tomography scans from the ⁶⁴Cu-SAR-bisPSMA PET/CT will be available for anatomic correlation.

The readers will be required to evaluate the PET scans individually for the presence of pathological ⁶⁴Cu-SAR-bisPSMA uptake in the prostate bed/gland, pelvic lymph nodes, extra pelvic lymph nodes, visceral/soft tissue and bone. The same ⁶⁴Cu-SAR-bisPSMA PET-positive lesion definition will be applied as for the local interpretation. Lesions that do not meet the criteria for a positive lesion but are deemed suspicious for PC will be recorded as equivocal. The number of lesion(s) in each anatomical subregion will be documented. The size (two axial dimensions), location, standardized uptake value (SUV)mean and max, lesion-to-background ratio and reader confidence level will be recorded for up to 15 soft tissue lesions and 10 bone lesions by the central readers.

The processes for image acquisition, transmittal, and interpretation are detailed in the Image Acquisition Manual and Imaging Review Charter.

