## 7.3 Handling of Missing Data

- Missing values for individual data points will remain as missing. Missing values will not be imputed and only observed values will be used in data analyses and presentations unless otherwise indicated. For the reference standard, expert panel adjudications will never be missing and will be assigned as "non-evaluable" if based on missing data. Sensitivity analyses will be performed for non-evaluable reference standard assessments.
- Where individual data points are missing, categorical data will be summarized based on reduced denominators (i.e., only patients with available data will be included in the denominators) unless otherwise indicated.

September 4, 2024 CONFIDENTIAL Page 17 of 46

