## • False Positive:

• A participant who does not meet the TP criteria and has at least one unequivocal Cu-SAR-bisPSMA PET-positive lesion and has an evaluable Reference Standard.

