#### 9.14.1 Primary Efficacy Analyses

The co-primary efficacy endpoints are the following:

- Participant-level CDR at Day 0.
- Participant-level CDR at Day 1.
- Region-level PPV at Day 0.
- Region-level PPV at Day 1.

September 4, 2024 CONFIDENTIAL Page 28 of 46

 $\underline{CDR}$  on a participant-level for each central reader is defined as the proportion of TP participants out of all scanned participants who had at least 1 evaluable reference standard datapoint collected and is calculated as:  $\overline{CDR} = \overline{TP}/(all\ scanned\ participants\ with at least 1 evaluable reference datapoint) x 100.$ 

Participants without a Cu-SAR-bisPSMA PET/CT scan at the specific timepoint (Day 0 or Day 1) will be excluded from the participant-level CDR calculation for that timepoint. Participants with non-evaluable participant-level Reference Standard results will be excluded from the CDR calculation

PPV is measured on a region-level (the primary endpoint will be calculated including all 5 regions as a whole) for each central reader and is defined as the proportion of TP regions out of all positive regions on the  $^{64}$ Cu-SAR-bisPSMA PET/CT scan with corresponding evaluable composite Reference Standard data and will be calculated as: PPV = TP/(TP + FP) x 100, where FP = False Positive.

Regions that are not positive on the Cu-SAR-bisPSMA PET/CT scan at a specific timepoint will be excluded from the region-level PPV for that timepoint. PET/CT positive regions without corresponding evaluable composite Reference Standard results will also be excluded.

The anatomic regions for the PPV calculation are the following:

- Region 1 = Prostatic
- Region 2 = Pelvic lymph nodes
- Region 3 = Extra pelvic lymph nodes
- Region 4 = Visceral/soft tissue
  - o This region is incorrectly labeled as Region 5 in the raw data and will be recoded
- Region 5 = Bone
  - o This region is incorrectly labeled as Region 4 in the raw data and will be recoded

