## 9.14.2 Secondary Efficacy Analyses

The following secondary analyses will be performed in a similar manner as the primary analysis, and will be summarized by central reader with point estimates and exact Clopper-Pearson 95% CI in the FAS and repeated with the PP analysis set:

- Participant-level PPV at Day 0 and Day 1;
  - $\circ$  PPV = TP/(TP + FP) x 100.
- Participant-level Detection Rate (DR) at Day 0 and Day 1;
  - o DR = (number of participants with positive Cu-SAR-bisPSMA PET/CT scan)/(all scanned participants with a Cu-SAR-bisPSMA PET/CT scan) x 100.

September 4, 2024 CONFIDENTIAL Page 30 of 46

- Participant-level False Positive Rate (FPR) on Day 0 and Day 1;
  - $\circ$  FPR = FP/(all scanned participants with a positive Cu-SAR-bisPSMA PET/CT scan and an evaluable reference standard) x 100.
- Region-level FPR at Day 0 and Day 1;
  - $\circ$  FPR = FP regions/(all positive regions on the Cu-SAR-bisPSMA PET/CT scan and an evaluable reference standard) x 100.
- Participant-level discrepant PET negative rate between Day 0 and Day 1 for reference standard positive participants.
- Discrepant PET negative rate;
  - O Discrepant PET negative rate = (number of participants with participant-level discrepancy in Cu-SAR-bisPSMA results between Day 0 and 1) / (all participants with a positive reference standard) x 100.
- Participant-level True Negative Rate (TNR) on Day 0 and Day 1;
  - $\circ$  TNR = TN/(TN+FP) x 100.
- Participant-level Apparent Negative Predictive Value (ANPV; referred to as TNR in the study protocol) on Day 0 and Day 1;
  - o TN/(number of participants with a negative Cu-SAR-bisPSMA result)
- Region-level TNR at Day 0 and Day 1.
  - $\circ$  TNR = TN/(TN+FP) x 100.
- Region-level Apparent Negative Predictive Value (ANPV; referred to as TNR in protocol) at Day 0 and Day 1;
  - o TN/(number of regions with a negative Cu-SAR-bisPSMA result).

Note: Discrepant Day 0 and Day 1  $^{64}$ Cu-SAR-bisPSMA PET/CT results (results differ within subregion from Day 0 and Day 1 within the same central reader) will also be listed.

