#### 9.14.3.2 Function of Baseline and Other Variables of Interest

CDR, participant- and region-level PPV, and DR of both the Day 0 and Day 1 scans will be summarized by the following variables:

- PSA at baseline:  $<0.5, 0.5 <1.0, 1.0 <2.0, 2.0 <5.0, \ge 5.0 \text{ ng/mL}.$
- PSA doubling time at baseline (PSADT):  $<3.0, 3.0-8.9, 9.0-14.9, \ge 15.0$  months.
- PSA velocity at baseline: 0 to <0.05, 0.05 to <0.10, 0.10 to <0.20, \ge 0.20 ng/mL/y.
- Testosterone at baseline: <230, 230-350, >350 ng/dl.
- Standardized uptake value (SUV) max:  $\leq 2, 2 < 5, 5 < 10, \geq 10$ .
- Initial treatment received (2 categories): radical prostatectomy OR radiation therapy, cryotherapy and brachytherapy.
- Reference Standard Level of Evidence Used: Level 1, Level 2, Level 3
  - Level 1 = histopathology (regardless of imaging results or PSA response being available).
  - Level 2 = imaging results (regardless of PSA response being available) but no contributing histopathology information,

September 4, 2024 CONFIDENTIAL Page 32 of 46

- Level 3 = PSA response only ((i.e., no contribution of histopathology or imaging result information (participant-level only)).
- Size of largest lesion (long axis) identified on  $^{64}$ Cu-SAR-bisPSMA PET/CT central reader scan:  $0 <0.5, 0.5 <1.0, \ge 1.0$  cm.
- Time to Cu-SAR-bisPSMA PET/CT scan from dosing (Day 0 only): 1 − 2 hours, 2 -4 hours.

CDR, participant and region-level PPV, and DR will be summarized for each level of the baseline categorical variables with CDR, PPV, and DR values in each category by central reader. Region-level parameters will only be summarized for the "All regions" category and not the individual regions.

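### Summarising DR and CDR by SUVmax and lesion size conditions both rates on the scan's own finding; only PPV is interpretable by these two variables

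*SAP*

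**What the plan says.** SAP 9.14.3.2 lists the variables by which CDR, participant- and region-level PPV, and DR of the Day 0 and Day 1 scans are summarised. Two are measurements from the study scan itself:

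- "Standardized uptake value (SUV) max", in four bands cut at 2, 5 and 10;
- "Size of largest lesion (long axis) identified on" the study PET/CT as read centrally, in three bands: 0 to under 0.5 cm, 0.5 to under 1.0 cm, and 1.0 cm or more.

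The section then says that "PPV, and DR will be summarized for each level of the baseline categorical variables", by central reader. It gives no category or rule for a participant with no lesion, and does not say which day's scan supplies the value.

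The rates are defined elsewhere. SAP 9.14.2 has "DR = (number of participants with positive" scans over all scanned participants. SAP 9.14.1 defines CDR as the "proportion of TP participants out of all scanned participants who had at least 1 evaluable reference standard datapoint collected". In SAP 7.8 a participant-level false positive fails the true-positive criteria but has an unequivocal "PET-positive lesion and has an evaluable Reference Standard". A scan with only equivocal lesions counts as negative.

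Protocol 7.3.2.2 says that size and SUV "will be recorded for up to 15 soft tissue lesions and 10 bone lesions by the central readers". They are therefore per-lesion records. SAP 7.3 says that, where individual data points are missing and nothing else is indicated, "categorical data will be summarized based on reduced denominators".

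Protocol 10.4.5.3 lists SUV mean and max and lesion-to-background ratio among the baseline variables for this analysis. SAP Table 3 removes lesion-to-background ratio; SAP 9.14.3.2 keeps SUVmax and adds lesion size.

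**The concern.** A baseline variable such as PSA has a value for every participant whatever the scan shows. SUVmax and largest-lesion size do not: they come into being when the reader marks a lesion, which is nearly the same event as the DR numerator. Banding DR by them asks how often a lesion was detected among participants in whom a lesion was detected. CDR has the same defect. Once lesion-free negatives leave its denominator, what remains is essentially true positives over true plus false positives, which is PPV under another name.

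The risk is misreading. Protocol 2.5.1 hypothesises that delayed imaging may find smaller lesions. A table with high DR for lesions under 0.5 cm, by day and by reader, could be taken as evidence of small-lesion sensitivity. The study assigns no false negatives (Protocol 7.5.2, SAP 7.8), so it has no sensitivity estimate to set against that reading.

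**Working it through.** **Inputs.** SAP 4.2 and Protocol 10.3 give participant-level CDR 42%, PET-positive share 65%, 1.3 positive regions per positive participant, region-level PPV 65%, 40 evaluable participants and 20% non-evaluable. The share of participants with only equivocal lesions is not given; I assume 0% to 15%. I also take the 65% positive share to hold among the evaluable participants.

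**The plan's own figures reproduce.**

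- CDR: with n = 40, the exact 95% lower limit first exceeds 20% at 14 true positives (20.6%). Power at a true 42% is 85.5%, against a stated figure above 85%.
- Region-level PPV: 40 × 0.65 × 1.3 = 33.8, about 34 regions. The lower limit first exceeds 40% at 20 of 34 (40.7%). Power at 65% is 82.6%, against a stated figure above 80%.
- Total: 40/(1 − 0.20) = 50.

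**Overall rates.** Of 40 evaluable participants, 40 × 0.65 = 26 are positive and 14 negative, with 40 × 0.42 = 16.8 expected true positives. DR is 26/40 = 65%, CDR is 16.8/40 = 42%, and implied participant-level PPV is 16.8/26 = 0.42/0.65 = 64.6%.

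**Case 1: participants without a lesion drop out.** Let e be the share of all participants who have only equivocal lesions and carry a value. Taken over all bands together:

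DR = 0.65/(0.65 + e), CDR = 0.42/(0.65 + e), PPV = 0.42/0.65.

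| e (assumed) | DR | CDR | PPV |
|---|---|---|---|
| 0% | 100% | 64.6% | 64.6% |
| 2% | 97.0% | 62.7% | 64.6% |
| 5% | 92.9% | 60.0% | 64.6% |
| 10% | 86.7% | 56.0% | 64.6% |
| 15% | 81.3% | 52.5% | 64.6% |

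In every row DR and CDR exceed the planned 65% and 42%. PPV does not move, because it is already conditional on a positive scan.

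**Case 2: participants without a lesion are coded 0 into the lowest band.** Spread the 26 positives evenly over the bands (an assumption) and place all 14 negatives in the lowest.

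- Size, three bands: 26/3 = 8.67 positives per band; lowest-band DR = 8.67/(8.67 + 14) = 38%.
- SUVmax, four bands: 26/4 = 6.5 per band; lowest-band DR = 6.5/(6.5 + 14) = 32%.
- All higher bands: 100%.

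The lowest-band figure depends on the spread. With 10% of positives there, DR is 2.6/16.6 = 16%; with 50%, 13/27 = 48%. Either way the coding produces the gradient.

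**The case against.** The strongest opposing case is that the size of the effect is not fixed by the documents. Most of that stands.

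- **DR near 100% in every band.** A reader might infer this, including for lesions under 0.5 cm. The documents do not establish it. Equivocal lesions are recorded, and nothing limits size and SUV to unequivocal ones, so some negatives may carry values. If equivocal lesions tend to be small or faint, the dilution would fall mainly in the lowest bands. Coding negatives as 0 would make the lowest band artificially low instead.
- **CDR equal to PPV.** This is exact only if no equivocal-only participant carries a value and no inconclusive reference enters the CDR denominator. SAP 7.8 leaves inconclusive results unassigned, but SAP 9.14.1 does not expressly exclude them.
- **Scan day.** If the value may come from either day, someone negative on Day 0 and positive on Day 1 enters the Day 0 denominator, which softens the circularity.
- **The 65% PPV.** The stated figure is region-level. The participant-level value is only implied by 0.42/0.65.
- **Lesion-to-background ratio.** A reader might infer that the SAP removed it because of circularity. Table 3 says only that it was unnecessary or uninformative here, so it is not a precedent for this argument.
- **Impact.** The analysis is exploratory and no formal testing is planned. Overall DR and CDR are reported separately. The protocol prespecifies the SUV breakdown, so removing part of it is a departure.

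Under either coding of lesion-free participants with same-day values, the rates remain conditioned on the scan's own result. An either-day value only weakens this.

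**Conclusion.** The concern holds in this form: DR and CDR banded by SUVmax or largest-lesion size are conditioned on the scan result that they are meant to describe.

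Under the SAP 7.3 default, DR is inflated from 65% towards 100% and CDR from 42% towards 64.6%. The assumed equivocal-only range of 0% to 15% gives 100% to 81% and 65% to 52.5% across bands. Under zero-coding, the higher bands sit at or near 100% and the lowest is artificially low, at about 38% for size and 32% for SUVmax with an even spread. These figures rest on the plan's 65% and 42%, on same-day values, and on equivocal shares and a band spread that the documents do not supply.

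It would go too far to infer that the whole subsection is invalid or that the main results are compromised. PPV by the same variables is sound, the PSA, testosterone and initial-treatment breakdowns do not share this problem, and primary endpoints and sample size are untouched. This is a desirable correction to exploratory tables.

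**What to change.** In SAP 9.14.3.2, for SUVmax and lesion size only:

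1. Report participant-level and region-level PPV, and remove DR and CDR.
2. State that the value is taken from the same reader's scan on the same day as the rate being summarised.
3. Add a row to SAP Table 3, because Protocol 10.4.5.3 prespecifies CDR, PPV and DR by SUV. Give as the reason that these variables are defined only when a lesion is recorded.

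A no-lesion row or a footnote would be a lighter change, but it would only make the conditioning visible: DR in that row would be 0% by construction, and the other rows would remain largely uninformative.

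The cost is a small departure from a protocol-listed exploratory analysis, with fewer tables and no new data. Little is lost, since SAP 9.14.3.3 already compares SUV and lesion size between true and false positives.

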10.3 Determination of Sample Size

The co-primary endpoints include participant-level correct detection rate (CDR) or true positive detection rate and region-level positive predictive value (PPV).

The assumed participant-level CDR of ⁶⁴Cu-SAR-bisPSMA PET/CT imaging is 42% in participants with biochemical recurrence of PC. A sample size of 40 participants is estimated to provide more than 85% power to achieve a lower boundary of a 2-sided 95% exact binomial confidence interval (CI) about the estimated CDR that exceeds 20%. Accounting for a 20% non-evaluable rate (including lost to follow-up), approximately 50 participants will need to undergo ⁶⁴Cu-SAR-bisPSMA PET/CT in this study.

For the co-primary efficacy endpoint of region-level PPV, assuming 65% of participants are estimated to have ⁶⁴Cu-SAR-bisPSMA PET/CT positive findings in this target population and each participant with positive findings has an average of 1.3 positive regions, then 40 participants are expected to produce approximately 34 positive regions. The assumed region-level PPV rate of ⁶⁴Cu-SAR-bisPSMA PET/CT imaging is approximately 65% in all PET positive regions. Therefore, a sample size of 40 participants (i.e., approximately 34 positive regions) is estimated to provide more than 80% power to achieve a lower boundary of a 2-sided 95% exact binomial CI about the estimated region-level PPV that exceeds 40%.

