10.4.5.3 Exploratory Efficacy Analyses

The exploratory efficacy endpoints include the following:

- Proportion of participants with any change in intended PC treatment due to either the Day 0 or Day 1 scan;
- Composite CDR, PPV and DR of the Day 0 and Day 1 scan;

- CDR, participant- and region-level PPV and DR of the Day 0 and/or Day 1 scan as a function of baseline variables;
- Relationship between PET-positivity (biodistribution measures such as SUVs and lesion-to-background ratio), versus true/false positivity and as a function of lesion location and size;
- Difference in the number of lesions detected per participant on the Day 0 versus the Day 1 scan;
- Lesion-level overall agreement rate on the Day 0 and Day 1 scans, on the Day 0 and reference scans, and on the Day 1 and reference scans;
- PSA over time and change from baseline;
- PSA velocity and PSA doubling time (PSADT) at the end of the study and at baseline.

Binary exploratory endpoints will be summarized with points estimates and corresponding 2-sided 95% exact binomial CIs based on the FAS.

Difference in the number of lesions detected per participant on the Day 0 versus the Day 1 scan will be summarized descriptively and compared using a paired *t*-test. Other exploratory endpoints including PSA value at each scheduled time point and change from baseline, PSA velocity, and PSADT will be summarized using descriptive statistics.

Descriptive statistics, graphical methods, and statistical modeling as appropriate may be used to explore the relationship between PET-positivity (biodistribution measures such as SUVs and lesion-to-background ratio) and true/false positivity.

In addition, CDR, PPV and DR will also be assessed as a function of the following baseline variables:

- PSA at baseline prior to the scan (<0.5, 0.5 <1.0, 1.0 <2.0, 2.0 <5.0, ≥5);
- PSADT;
- PSA velocity;
- Testosterone at baseline;
- SUV mean and max;
- Lesion-to-background ratio;
- Initial Treatment Received.

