## 3.1.3 Exploratory Study Objectives and Endpoints

Objective	Endpoint		
To evaluate the reproducibility of the  Cu-SAR-bisPSMA PET/CT readings and consistency among readers.	
 
Intra-reader variability per reader.
 
Inter-reader variability expressed by kappa statistics.
 
		
■ To assess the impact of  Cu-SAR-bisPSMA PET/CT on disease management.	
 
Proportion of participants with any change in intended PC treatment due to either the Day 0 or Day 1 scan.
 
		

 
Composite performance of the Day 0 and Day 1 Cu-SAR- bisPSMA PET/CT scans.
 
	Composite CDR defined as the proportion of TP participants on the Day 0 and/or Day 1 scan out of all participants with a Day 0 and/or Day 1 scan.		
	
 
Composite participant/region-level PPV defined as the proportion of TP participants/regions on the Day 0 and/or Day 1 scan out of all participants/regions with a positive Day 0 and/or Day 1 scan.
 
		
	
 
Composite DR defined as the proportion of participants with a positive Day 0 and/or Day 1 scan out of all participants with a Day 0 and/or Day 1 scan.
 
		
■ To determine the effect of baseline variables on the CDR, PPV and DR of  Cu-SAR-bisPSMA PET/CT.	
 
CDR, participant- and region-level PPV and DR of the Day 0 and/or Day 1 scan as a function of baseline variables.
 
		
■ To explore the correlation between  Cu-SAR-bisPSMA PET-positivity and Reference Standard results.	
 
Relationship between PET-positivity (biodistribution measures such as SUVs and lesion-to-background ratio), versus true/false positivity and as a function of lesion location and size.
 
		

September 4, 2024 CONFIDENTIAL Page 13 of 46

- To assess the lesion-level performance of Cu-SARbisPSMA PET/CT.
- Difference in the number of lesions detected per participant on the Day 0 versus the Day 1 scan.
- Overall agreement rate on the Day 0 and Day 1 scans, defined as the number lesions with matching subregion divided by the total number of lesions identified across all scans by either imaging.
- Overall agreement rate on the Day 0 and reference scans, defined as the number lesions with matching subregion divided by the total number of lesions identified across all scans by either imaging.

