#### 4.0 HYPOTHESIS TEST AND SAMPLE SIZE ESTIMATION

## 4.1 Hypothesis Test

No formal hypothesis testing is planned. All statistical testing and associated p-values are presented without controlling for the alpha level.

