## 4.2 Sample Size Estimation

Approximately 50 participants are planned to be enrolled into the study. The assumed CDR of Cu-SAR-bisPSMA PET/CT imaging is 42% in this population. A sample size of 40 participants is estimated to provide more than 85% power to achieve a lower boundary of a 2-sided 95% exact binomial confidence interval (CI) about the estimated CDR that exceeds 20%. Accounting for a 20% non-evaluable rate, approximately 50 participants will need to undergo Cu-SAR-bisPSMA PET/CT in this study.

Additionally, for the co-primary efficacy endpoint of region-level PPV, assuming 65% of participants are estimated to have Cu-SAR-bisPSMA PET/CT positive findings in this target population and each participant with positive findings has an average of 1.3 positive regions, then 40 participants are expected to produce approximately 34 positive regions. The assumed region-level PPV rate of Cu-SAR-bisPSMA PET/CT imaging is approximately 65% in all PET positive regions. Therefore, a sample size of 40 participants (i.e., approximately 34 positive regions) is

September 4, 2024 CONFIDENTIAL Page 14 of 46

estimated to provide more than 80% power to achieve a lower boundary of a 2-sided 95% exact binomial CI about the estimated region-level PPV that exceeds 40%.

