#### 9.14 Efficacy Analyses

All efficacy endpoints will be assessed using the FAS with supportive analyses performed with the PP analysis set for the primary efficacy endpoints and selected secondary endpoints. For definitions of Cu-SAR-bisPSMA PET/CT positive status criteria see Section 7.7 and for definitions of assessment of Cu-SAR-bisPSMA results against the Reference Standard results, see Section 7.8. Alpha level is set to 0.05 for all p-values but alpha is not controlled, and p-values are considered exploratory.

All analyses that are considered "region-level" will be conducted in 2 ways (unless otherwise specified): the analysis will be conducted on all 5 regions as a whole (labeled as "All Regions") and by-region individually, for 6 total calculations.

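### Baseline PSA and the other continuous baseline variables are related to CDR, PPV and DR only through category tables, so the exploratory objective gets no effect estimate; a short exploratory model on the recorded values would supply one cheaply

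*SAP*

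**What the plan says.** SAP 3.1.3 gives the exploratory objective as "To determine the effect of baseline variables on the CDR, PPV and DR of" the agent's PET/CT. Protocol 10.4.5.3 carries it forward: "CDR, PPV and DR will also be assessed as a function of the following baseline variables". The protocol fixes the PSA bands there, but lists PSADT, PSA velocity and testosterone without cut points.

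SAP 9.14.3.2 supplies the cut points and the method: "CDR, participant and region-level PPV, and DR will be summarized for each level of the baseline categorical variables", by central reader, for the Day 0 and Day 1 scans. Baseline PSA has five categories, PSADT four, PSA velocity four, testosterone three and time from dose to the Day 0 scan two. The section names no regression, trend test or other estimate that runs across categories. Protocol 10.4.5.3 does allow statistical modelling, but attaches it to the relation between uptake measures and true/false positivity, not to these variables.

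SAP 9.14.3.6 separately summarises total PSA, PSA velocity and PSADT as uncategorised values, including within participants classed as true positive (TP), false positive (FP) or true negative (TN). On testing in general, SAP 4.1 says "No formal hypothesis testing is planned", and SAP 9.14 says "Alpha level is set to 0.05 for all p-values but alpha is not controlled".

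**The concern.** The objective asks for an effect and the analysis returns a list of proportions. With five PSA categories a reader sees five imprecise figures per reader and timepoint. There is no summary of whether, or how steeply, detection rises with PSA, and no interval for such a gradient. The variables are recorded on a continuous scale, and the analysis of CDR, PPV and DR uses neither the recorded values nor, formally, the order of the categories.

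This matters more for PSA than for the other variables, because the protocol's background section argues for the agent partly on its potential in men with low PSA. How detection depends on PSA is therefore a natural question for the study report, and the plan leaves it to visual comparison of small cells.

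**Working it through.** **Inputs from the documents.** SAP 4.2: "Approximately 50 participants are planned to be enrolled into the study", and "A sample size of 40 participants is estimated to provide more than 85% power" for CDR after a 20% non-evaluable rate. Protocol 10.3: the assumed CDR of "PET/CT imaging is 42% in participants with biochemical recurrence of PC". Both sections assume that 65% of participants are PET-positive, with 1.3 positive regions each.

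**The plan's own figures reproduce.** With 40 men, the exact 95% lower bound first exceeds 20% at 14 true positives, and power at 42% is 85.5%. Regions: 40 × 0.65 × 1.3 = 33.8, about 34; the lower bound first exceeds 40% at 20 regions, and power at 65% is 82.6%. Enrolment: 40 / (1 − 0.20) = 50. No power is stated for the baseline-variable analysis.

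**Average category sizes** (actual sizes are unknown and may be uneven):

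| Denominator | PSA (5) | PSADT, velocity (4) | Testosterone (3) | Scan time (2) |
|---|---|---|---|---|
| DR, 50 | 10 | 12.5 | 16.7 | 25 |
| CDR, 40 | 8 | 10 | 13.3 | 20 |
| Participant-level PPV, 40 × 0.65 = 26 | 5.2 | 6.5 | 8.7 | 13 |

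**Precision within a category.** The exact (Clopper-Pearson) limits for x of n are the 2.5% point of Beta(x, n − x + 1) and the 97.5% point of Beta(x + 1, n − x). For 3 of 8 these are Beta(3, 6) and Beta(4, 5), giving 8.5% to 75.5%. Likewise 2 of 5 gives 5.3% to 85.3%, 4 of 10 gives 12.2% to 73.8%, and 10 of 25 gives 21.1% to 61.3%.

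**How much information the recorded values hold, for PSA on CDR.** The documents give neither a PSA distribution nor a slope, so both are assumed: lognormal PSA with median 0.8 or 1.5 ng/mL and SD of ln PSA 1.2, and an odds ratio (OR) of 1.4 to 2.0 per doubling. The intercept is set so that the marginal CDR is 42% with n = 40. There were 1,500 simulated trials per scenario with 299 permutations each. Three tests were compared: an unordered chi-square over the SAP's five PSA categories, a trend test over the same categories, and a score test on log2 PSA.

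| OR per doubling | Unordered, 5 categories | Trend, same categories | log2 PSA |
|---|---|---|---|
| 1.4 | 21–22% | 32–34% | 39–40% |
| 1.6 | 35–40% | 56% | 63–64% |
| 1.8 | 51% | 71–72% | 78–79% |
| 2.0 | 64–65% | 83% | 88–89% |

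The continuous test gains about 17 to 29 points over the unordered test. A separate run of 1,000 trials per scenario gave 18 to 28. Over the trend test it gains 5 to 8 points in this table and about 4 to 9 across runs. Type I error was 4% to 6% for the unordered and continuous tests.

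**Analytic check.** Five equal-sized categories of a normal covariate retain 0.897 of the information. If the continuous test has 80% power, its noncentrality is (1.960 + 0.842)² = 7.85, and 7.85 × 0.897 = 7.04 remains. On 4 df that gives 54.3% power (25.7 points lower). On 1 df, as in a trend test, it gives 75.6% (4.4 points lower). Most of the gap comes from ignoring the order of the categories, and only a small part from the cutting itself.

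**The case against.** The strongest reply is that this is a descriptive table for an exploratory objective in a study of about 50 men. The endpoint asks for the rates as a function of baseline variables, the protocol fixed the PSA bands, and an ordered five-row table shows a gradient to anyone who reads down it. That is a legitimate choice, and it limits the point to an improvement. It does not supply an effect estimate. The SAP's position on testing does not rule one out either, since sections 9.14.3.3 and 9.14.3.4 already use exploratory Wilcoxon and chi-square tests.

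Several stronger readings are tempting, and the documents do not support them:

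- A reader might infer that the plan loses 17 to 29 points of power. No test is planned in 9.14.3.2, so there is no power to lose. The figure compares two tests that are not in the SAP.
- A reader might carry that range over to all five variables and all three rates. It was computed for PSA on CDR alone. Across other category counts and denominators, again with assumed effects, the gap to an unordered test runs from about 9 to 30 points.
- A reader might say that the recorded PSA values are never used. SAP 9.14.3.6 does use them, descriptively and grouped by outcome. For testosterone and scan time there is no comparable summary by outcome.
- A reader might say that every category holds only a few men. That is fair for PSA and for PPV, but not for scan time (20 to 25 on average) or testosterone (13 to 17 for CDR and DR).

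Modelling everything would also have a cost. Four predictors × 3 rates × 3 readers × 2 timepoints is 72 models, plus 9 for scan time on Day 0, or 81 in all, with alpha uncontrolled and only about 26 men behind each PPV model.

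**Conclusion.** The point holds as a cheap improvement. SAP 9.14.3.2 reports separate proportions with no model or trend, so the objective of determining an effect gets no effect estimate. PSA cells average about 8 men for CDR and about 5 for participant-level PPV.

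For PSA on CDR the information left unused is worth about 17 to 29 points of power against an unordered comparison and about 4 to 9 points against a trend analysis of the same categories. Both ranges rest on the assumed PSA distribution, a log-linear effect, OR 1.4 to 2.0 per doubling, and 40 evaluable men. No primary or secondary conclusion is affected.

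**What to change.** Keep the category tables. Add to SAP 9.14.3.2, per central reader and timepoint, an exploratory single-predictor Firth (penalised) logistic regression of participant-level CDR status and DR status on:

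- log2 baseline PSA;
- the baseline PSA log-slope, ln 2 / PSADT. From SAP 7.6 this is [ln(screening PSA) − ln(oldest PSA within 12 months)] / months between them. It is zero for a flat PSA and negative for a falling one, whereas PSADT itself is undefined or negative.

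Report the odds ratio with its 95% profile-likelihood CI and a fitted curve, labelled exploratory. Name the unit for the log-slope and the number of men without a usable earlier PSA. This is 2 predictors × 2 rates × 3 readers × 2 timepoints = 24 models. PSA velocity, testosterone, scan time and PPV can be left as options.

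The cost is a paragraph of SAP text and a little programming on data already collected. SAP 1.0 provides for amendment before database lock; after lock, the addition should be described in the study report as made after the plan. The downsides to state are:

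- Linearity on the logit scale is assumed, though the retained tables allow a check.
- Multiplicity is not controlled.
- Precision is low: about 0.42 × 40 = 17 true positives inform each CDR model, and at OR 1.4 per doubling the continuous test had only 39% to 40% power.
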